10.4.4 Supportive and Sensitivity analyses

Not applicable

10.5 Secondary objectives

10.5.1 Key secondary objective

The key secondary objective for this study is to evaluate the ocular safety of deferasirox FCT and phlebotomy over 24 months.

To characterize long-term ocular safety, the incidence of treatment-emergent ocular AEs (new or worsening from baseline) will be summarized categorically by system organ class and/or preferred term, overall and by severity, type of AE, and relation to study treatment. Ocular AEs will be defined in the study Statistical Analysis Plan (SAP).

Treatment-emergent AEs are defined as AEs started during on-treatment period: from the day of the first dose of study medication or the first phlebotomy to 30 days after the last dose of study medication or last phlebotomy.

No hypothesis will be tested for this key secondary objective.

10.5.2 Secondary efficacy objective(s)

The secondary efficacy objective is time to first response of achieving $SF \le 100 \ \mu g/L$. For this analysis, the following censoring rule will be applied:

For patients who did not achieve a response, they will be censored at the earliest of the following dates:

- Death or discontinuation date due to any reason
- Last SF assessment.

Kaplan-Meier estimates will be presented. Median time to response (as well as 25th and 75th percentiles) will be presented along with 95% confidence intervals for the two arms.

10.5.3 Secondary safety objectives

Secondary safety objectives include:

- Safety and tolerability of deferasirox FCT and phlebotomy over 24 months
- Change from baseline in visual acuity (ETDRS), intra-ocular pressure, retina or/and optic nerve abnormalities, and lens abnormalities at months 6, 12, 18, and 24.
- Safety and tolerability of deferasirox FCT in patients who interrupt due to $SF \le 100 \ \mu g/L$ and re-initiate therapy when > 300 $\mu g/L$.

See Section 3 for details on safety objectives. Descriptive statistics will be provided for all safety objectives using the Safety set.

Safety and tolerability between deferasirox FCT and phlebotomy during 24 months of study period will be assessed through the incidence of new or worsening AEs, abnormal and clinically significant laboratory findings, and other abnormal safety findings. See Section 10.5.3.2, Section 10.5.3.3, and Section 10.5.3.4 for details.

To assess the effect of deferasirox FCT and phlebotomy, the change from baseline in visual acuity (ETDRS), intra-ocular pressure, retina or/and optic nerve abnormalities, and lens abnormalities will be summarized descriptively by treatment and by visit. The detailed analysis will be detailed in the SAP.

Incidence of AEs in patients who interrupted deferasirox FCT at least once due to $SF \le 100 \mu g/L$ and re-initiated $\ge 300 \mu g/L$ will be tabulated and listed. The detailed analysis will be detailed in the SAP.

10.5.3.1 Analysis set and grouping for the analyses

For all safety analyses, the safety set will be used. All listings and tables will be presented by treatment group.

The overall observation period will be divided into three mutually exclusive segments:

- 1. Pre-treatment period: from the day of a patient's informed consent to the day before the first dose of study medication or first phlebotomy
- 2. On-treatment period: from the day of the first dose of study medication to 30 days after the last dose of study medication or last phlebotomy
- 3. Post-treatment period: starting at day 30+1 after last dose of study medication or last phlebotomy.

10.5.3.2 Adverse events (AEs)

Summary tables for AEs will include only AEs that started or worsened during the on-treatment period, the treatment-emergent AEs.

The incidence of all treatment-emergent AEs (new or worsening from baseline) in both arms will be summarized by SOC and/or PT, severity, type of AE, relation to study treatment. CTCAE grade will not be used.

All deaths (on-treatment and post-treatment) will be summarized.

All AEs, deaths and SAEs (including those from the pre and post-treatment periods) will be listed and those collected during the pre-treatment and post-treatment period will be flagged.

Project-specific AESI are defined in the case retrieval strategy (CRS) with regular updates whenever necessary.

Specific groupings of AESI will be considered, and the number of patients with at least one event in each grouping will be reported. Such groups consist of AEs for which there is a specific clinical interest in connection with deferasirox. Certain AEs may be reported within multiple groupings/AESI.

AESI are defined by MedDRA terms.

SAEs, non-SAEs and AESI during the on-treatment period will be tabulated.

10.5.3.3 Laboratory abnormalities

All laboratory values will be converted into SI units and reported by the severity grade, using low/normal/high classifications based on laboratory normal ranges, and by notable/extended ranges for selected parameters (see Table 10-1).

Parameter	Criteria
Absolute neutrophils	< 1.5×10 ⁹ /L (extended range < 0.5×10 ⁹ /L)
Platelets	< 100×10 ⁹ /L (extended range < 50×10 ⁹ /L)
Hemoglobin	< 100 g/L
ALT and AST	> 5× ULN and > 2× baseline (extended range > 10× ULN and > 2× baseline)
Total bilirubin	> 2 mg/dL
Serum creatinine	> 33% increase from baseline and > ULN at 2 consecutive measurements at least 7 days apart
Creatinine clearance	< 60 mL/min at 2 consecutive measurements at least 7 days apart (extended range < 40 mL/min)
Urinary protein/creatinine ratio	≥ 1.0 mg/mg at 2 consecutive measurements at least 7 days apart

 Table 10-1
 Criteria for clinically notable and extended notable laboratory ranges

The following summaries will be generated separately for hematology, biochemistry, and urinary laboratory tests:

• Shift tables using normal/notable/extended ranges to compare baseline to the worst ontreatment value • Listing of all laboratory data with values flagged to show the corresponding normal/notable/extended ranges (see Table 10-1 above).

10.5.3.4 Other safety data

Data from ECG and auditory examinations will be listed and summarized separately with descriptive statistics as appropriate for the Safety set. All new or worsened abnormalities will be recorded as AEs.

Vital signs

The change from baseline in systolic and diastolic blood pressures, pulse rate, temperature and weight will be summarized by scheduled visit with n, mean, SD, minimum, median, and maximum values.

A listing will be provided for all vital signs and weight. Notable values will be flagged, according to criteria in Table 10-2.

Table 10-2	Definition of notable	ranges for	vital signs and	weight
------------	-----------------------	------------	-----------------	--------

Parameter	Criteria for notable ranges
Systolic blood pressure	\geq 180 mmHg / \leq 90 mmHg with increase / decrease from baseline \geq 20 mmHg
Diastolic blood pressure	\geq 105 mmHg / \leq 50 mmHg with increase / decrease from baseline \geq 15 mmHg
Pulse rate	\geq 120 bpm / \leq 50 bpm with increase / decrease from baseline \geq 15 bpm
Weight	≥ 10% increase

10.5.3.5 Supportive analyses for secondary objectives

Not applicable

10.5.3.6 Tolerability

Not applicable

10.5.4 Pharmacokinetics

Not applicable

10.5.4.1 Data handling principles

Not applicable

10.5.5 Biomarkers

Not applicable

10.5.6 Resource utilization

Not applicable

10.5.7 Patient-reported outcomes

Not applicable

10.6 Exploratory objectives

Not applicable

10.7 Interim analysis

Not applicable

10.8 Sample size calculation

The primary objective of the study is to estimate response rates and therefore the sample size is not based on power calculations. Sample size calculations were performed for the deferasirox FCT and phlebotomy arms to estimate the response rate (RR) with reasonable accuracy (half-width of 95% confidence interval).

Based on the Exjade study ICL670A2202, the patient dropout rate at month 6 (core study) is 24% and 12% at month 12 (optional extension phase). Assuming decreasing dropout rate over time and expected better patient compliance with deferasirox FCT formulation, a sample size of 100 patients in the FCT arm is expected to have at least 60 patients followed for 24 months to fulfil the FDA post-marketing requirement with regard to the ocular toxicity assessment in patients receiving deferasirox.

With a sample size of 100 on deferasirox FCT and 50 patients on phlebotomy, the projected half-widths of the 2-sided 95% confidence interval assuming various response rates are displayed in Table 10-3. The 95% confidence interval half-width extends at most to 0.096 and 0.136 in the deferasirox FCT and phlebotomy arms, respectively.

phiebotomy arms			
Response rate (RR)	Half-width of the 95% CI for deferasirox FCT N=100	Half-width of the 95% CI for phlebotomy N=50	
0.60	0.096	0.136	
0.65	0.093	0.132	
0.70	0.090	0.127	
0.75	0.085	0.120	
0.80	0.078	0.111	
0.85	0.070	0.099	
0.90	0.059	0.083	

Table 10-3Half-width of 95% CI of response rates in deferasirox FCT and
phlebotomy arms

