10.4.2 Statistical hypothesis, model, and method of analysis

The 2-sided 95% confidence interval will be constructed for the response rate by treatment arm based on the exact binomial distribution (Clopper-Pearson method).

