10.4.3 Handling of missing values/censoring/discontinuations

For the primary analysis, patients are considered responders if they meet response criteria for the primary endpoint on or before month 24. Any patient who discontinues prematurely before meeting such criterion will be considered a non-responder.

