#### 2.4.2 Statistical Hypothesis, Model, and Method of Analysis

RR is defined as the proportion of subjects whose  $SF \le 100 \ \mu g/L$  at any time on or before month 24 and the response rate will be summarized (proportion) by treatment arm along with two-sided exact binomial 95% CIs [Clopper and Pearson 1934]. The analyses will be descriptive only. No formal hypothesis testing is planned.

In addition, a box plot for serum ferritin by timepoint and treatment arm and line graph for individual subject values for serum ferritin by timepoint and treatment arm will be plotted.

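### The stated precision (half-widths of at most 0.096 and 0.136) is a normal-approximation figure for response rates of 0.60 or more; the planned Clopper-Pearson interval reaches 0.102 and 0.145

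*Protocol*

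**What the plan says.** Protocol 10.8 says that the sample size does not come from a power calculation and that the aim is to estimate each arm's response rate with reasonable accuracy, measured by the half-width of the 95% confidence interval. For planned arms of 100 (deferasirox) and 50 (phlebotomy) it adds: "the projected half-widths of the 2-sided 95% confidence interval assuming various response rates are displayed in Table 10-3". The table runs from 0.60 to 0.90 in steps of 0.05, and the text concludes: "The 95% confidence interval half-width extends at most to 0.096 and 0.136 in the deferasirox FCT and phlebotomy arms, respectively". SAP section 3 and its Table 3-1 repeat the statement and the values. Neither document names the interval method behind the table.

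For the analysis itself, Protocol 10.4.2 specifies an interval "based on the exact binomial distribution (Clopper-Pearson method"). SAP 2.4.2 agrees: the response rate is summarised "along with two-sided exact binomial 95% CIs [Clopper and Pearson 1934"]. The denominator is the Full Analysis Set (SAP 2.4.1), and Protocol 10.4.3 adds: "Any patient who discontinues prematurely before meeting such criterion will be considered a non-responder".

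**The concern.** Two things looked wrong. First, the tabulated half-widths have the size and symmetry of a normal approximation, whereas the planned interval is exact, wider and asymmetric. Second, a binomial half-width is largest at a rate of 0.50, so a maximum taken from a table that starts at 0.60 is not a maximum over all rates.

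Rates below 0.60 cannot be ruled out, at least for deferasirox. Patients who stop before responding count as non-responders. Protocol 10.8 cites dropout of 24% at month 6 and 12% at month 12 in an earlier study, and expects at least 60 of 100 patients to be followed for 24 months.

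The trial tests no hypothesis, so for the primary endpoint this table is the whole quantitative case for N=100 and N=50. If it is wrong, the design does not deliver the precision it claims with its own method.

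**Working it through.** **Inputs.** Two-sided 95% confidence, z = 1.96; n = 100 and 50; rates and stated half-widths from Table 10-3 (all Protocol 10.8). Interval method: Clopper-Pearson (Protocol 10.4.2, SAP 2.4.2). All randomised patients are in the denominator, so n is not reduced for dropout.

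**Step 1: reproduce the plan's figures.** Wald half-width = z·√(p(1−p)/n).
- p = 0.60, n = 100: 1.96 × √(0.24/100) = 0.0960 (stated 0.096).
- p = 0.60, n = 50: 1.96 × √(0.24/50) = 0.1358 (stated 0.136).

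The same formula gives all 14 cells to three decimals. Other methods do not. At 0.60 they give, for n = 100 and n = 50:
- Wald with continuity correction: 0.101 and 0.146
- Wilson: 0.094 and 0.131
- Clopper-Pearson: 0.0997 and 0.142

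**Step 2: apply the planned method.** With x = p·n responders, the lower limit is the 0.025 quantile of Beta(x, n−x+1) and the upper limit is the 0.975 quantile of Beta(x+1, n−x). The half-width is (upper − lower)/2.

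| Rate | N=100 stated | N=100 exact | N=50 stated | N=50 exact |
|---|---|---|---|---|
| 0.60 | 0.096 | 0.0997 | 0.136 | 0.1421 |
| 0.70 | 0.090 | 0.0937 | 0.127 | 0.1337 |
| 0.80 | 0.078 | 0.0826 | 0.111 | 0.1184 |
| 0.90 | 0.059 | 0.0636 | 0.083 | 0.0924 |

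At 0.60 the intervals are 0.497 to 0.697 (60/100) and 0.452 to 0.736 (30/50). Relative to the unrounded Wald value, the exact half-width is wider by:
- N=100: 0.0997/0.0960 − 1 = 4% at 0.60, rising to 0.0636/0.0588 − 1 = 8% at 0.90.
- N=50: 0.1421/0.1358 − 1 = 5% at 0.60, rising to 0.0924/0.0832 − 1 = 11% at 0.90.

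**Step 3: the maximum over all rates.** At p = 0.50 the Wald formula itself gives 1.96 × 0.5/√100 = 0.0980 and 1.96 × 0.5/√50 = 0.1386, both above the stated bound. Clopper-Pearson over every possible count peaks at 0.1017 (50/100) and 0.1447 (25/50). The exact half-width exceeds the stated bound for 34 to 66 responders of 100 and for 17 to 33 of 50, about a third of the possible counts in each arm.

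**Step 4: asymmetry.** At 0.90 the exact lower limits are 0.8238 (90/100) and 0.7819 (45/50). They lie 0.076 and 0.118 below the estimate, against stated half-widths of 0.059 and 0.083.

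**The case against.** The best defence is that the sentence follows directly on the reference to Table 10-3, so its natural reading is the largest value shown there. On that reading it is correct for the Wald formula. The maxima of 0.102 and 0.145 also combine two effects, the method and the move to a rate of 0.50. Like for like at 0.60, the gap is only 0.004 and 0.006. This is a fair account of how the gap arises, but it does not rescue the statement, because the planned interval exceeds the bound within the table too (0.0997 and 0.142).

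A second defence concerns consequence. No precision threshold is set beyond reasonable accuracy, N=100 is also supported by the aim of 60 patients followed for ocular safety, and the reported intervals will be Clopper-Pearson in any case. All of that is true, and it limits the importance of the point. The ocular argument, however, concerns the deferasirox arm only and gives no support to N=50 for phlebotomy.

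Third, the dropout figures come from a deferasirox study, and a patient may respond before stopping, so dropout is not the same as non-response. That stands: rates below 0.60 are plausible for deferasirox, not established, and the cited figures say nothing about phlebotomy. The plan gives no reason to exclude such rates in either arm.

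Finally, at N=50 some rates (0.65, 0.75, 0.85) do not correspond to whole numbers of responders, so an exact table needs a stated convention. That is right, and the fix should include one.

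**Conclusion.** The concern holds. Table 10-3 and SAP Table 3-1 show Wald half-widths, while both documents plan Clopper-Pearson intervals. The claimed maxima of 0.096 and 0.136 should be 0.0997 and 0.142 over the tabulated rates (0.60 to 0.90), or 0.102 and 0.145 over all rates. These figures assume the planned 100 and 50 patients are all in the denominator.

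The error is small and always in the favourable direction. It affects no test, endpoint or sample size, but it should be corrected because it is the only quantitative support given for the primary-endpoint precision.

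**What to change.** In Protocol 10.8 and SAP section 3:

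- Replace Table 10-3 and Table 3-1 with the Clopper-Pearson lower limit, upper limit and half-width for each rate.
- Add rows for rates from 0.40 to 0.55.
- State the convention where rate × 50 is not a whole number, for example the nearest whole count or beta quantiles evaluated at the fractional count.
- Restate the maximum half-widths as 0.102 (N=100) and 0.145 (N=50), reached at a rate of 0.50.

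The minimum acceptable change is to label the existing table as a normal approximation and confine the maximum to rates of 0.60 or more. That would be accurate but would still not give the precision of the planned interval.

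The cost is one sentence and one table in each document, with slightly less favourable stated precision. N and the analysis stay as they are.

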10.9 Power for analysis of key secondary variables

Not applicable

11 Ethical considerations and administrative procedures

11.1 Regulatory and ethical compliance

This clinical study was designed and will be implemented and reported in accordance with the ICH Harmonized Tripartite Guidelines for Good Clinical Practice, with applicable local regulations (including European Directive 2001/20/EC and US Code of Federal Regulations Title 21), and with the ethical principles laid down in the Declaration of Helsinki.

11.2 Responsibilities of the investigator and IRB/IEC/REB

The protocol and the proposed ICF must be reviewed and approved by a properly constituted Institutional Review Board/Independent Ethics Committee/Research Ethics Board (IRB/IEC/REB) before starting the study. In addition, the investigator is required to sign a protocol signature page confirming his/her agreement to conduct the study in accordance with these documents and all of the instructions and procedures found in this protocol and to provide access to all relevant data and records to Novartis monitors, auditors, Novartis Clinical Quality Assurance representatives, designated agents of Novartis, IRBs/IECs/REBs, and regulatory authorities as required.

11.3 Informed consent procedures

After providing written (witnessed, where required by law or regulation) IRB/IEC/REBapproved informed consent, eligible patients may be included in the study. The patient should indicate assent by personally signing and dating the written informed consent document.

Informed consent must be obtained before conducting any procedures described in the protocol. The process of obtaining informed consent should be documented in the patient source documents. The date when a subject's Informed Consent was obtained must be captured in the eCRF.

In a separate document, Novartis will provide investigators a proposed ICF that is considered appropriate for this study and complies with the ICH GCP guideline and regulatory requirements. Any changes suggested by the investigator must be agreed to by Novartis before ICF is submitted to the IRB/IEC/REB, and a copy of the approved version must be provided to the Novartis monitor after IRB/IEC/REB approval.

Women of child-bearing potential must be informed that taking the study medication may involve unknown risks to the fetus if pregnancy occurs during the study. In order to participate, they must adhere to the contraception requirement for the duration of the study. If there is any question that the patient will not reliably comply, they must not enter in the study.

Additional consent form

Not applicable

11.4 Discontinuation of the study

Novartis reserves the right to discontinue this study under the conditions specified in the clinical study agreement. Specific conditions for terminating the study are outlined in Section 4.4.

11.5 Publication of study protocol and results

Novartis is committed to following high ethical standards for reporting study results for its innovative medicine, including the timely communication and publication of clinical trial results, whatever their outcome. Novartis assures that the key design elements of this protocol will be posted on the publicly accessible database, e.g. ...clinicaltrials.gov, before starting the study. In addition, results of interventional clinical trials in adult patients are posted on ...novartisclinicaltrials.com, a publicly accessible database of clinical study results within 1-year of study completion (i.e., LPLV).

Novartis follows the ICMJE authorship guidelines (....icmje.org) and other specific guidelines of the journal or congress to which the publication will be submitted

Authors will not receive remuneration for their writing of a publication, either directly from Novartis or through the professional medical writing agency. Author(s) may be requested to present at poster or oral sessions at scientific congress; however, there will be no honorarium provided for such presentations.

As part of its commitment to full transparency in publications, Novartis supports the full disclosure of all funding sources for the study and publications, as well as any actual and potential conflicts of interest of financial and non-financial nature by all authors, including medical writing/editorial support, if applicable.

For the Novartis Guidelines for the Publication of Results from Novartis-sponsored Research, please refer tonovartis.com.

11.6 Study documentation, record keeping and retention of documents

Every participating site will maintain appropriate medical and research records for this trial, in compliance with Section 4.9 of the ICH E6 GCP, and regulatory and institutional requirements for the protection of confidentiality of subjects. As part of participating in a Novartis-sponsored study, each site will permit authorized representatives of the sponsor(s) and regulatory agencies to examine (and when required by applicable law, to copy) clinical records for the purposes of quality assurance reviews, audits and evaluation of the study safety and progress.
Source data are original records of clinical findings, observations, or other activities in a clinical trial necessary for the reconstruction and evaluation of the trial. Examples of these original documents and data records include, but are not limited to, hospital records, clinical and office charts, laboratory notes, memoranda, subjects' diaries or evaluation checklists, pharmacy dispensing records, recorded data from automated instruments, copies or transcriptions certified after verification as being accurate and complete, microfiches, photographic negatives, microfilm or magnetic media, x-rays, and subject files and records kept at the pharmacy, at the laboratories, and medico-technical departments involved in the clinical trial.

Data collection is the responsibility of the clinical trial staff at the site under the supervision of the Principal Investigator. The eCRF is the primary data collection instrument. The investigator should ensure the accuracy, completeness, legibility, and timeliness of the data reported in the eCRFs and all other required reports. Data reported on the eCRF, that are derived from source documents, should be consistent with the source documents or the discrepancies should be explained. All data requested on the eCRF must be recorded. Any missing data must be explained. For eCRFs an audit trail will be maintained by the system.

The investigator/institution should maintain the trial documents as specified in Essential Documents for the Conduct of a Clinical Trial (ICH E6 Section 8) and as required by applicable regulations and/or guidelines. The investigator/institution should take measures to prevent accidental or premature destruction of these documents.

Essential documents (written and electronic) should be retained for a period of not less than fifteen (15) years from the completion of the Clinical Trial unless Novartis provides written permission to dispose of them or requires their retention for additional time because of applicable laws, regulations and/or guidelines.

